9.4.3 Method of Assigning Subjects to Treatment Groups

At Study Baseline (Day 1), subjects will be assigned to treatments based on a computer-generated randomization scheme that will be reviewed and approved by an independent statistician. The ratio of randomization to LEM5, LEM10, or to PBO, will be approximately 1:1:1, and stratified by country and age group (<65 years old; ≥65 years old). At the 2nd randomization, those previously randomized to PBO will be randomized to either LEM5 or LEM10 on an approximately 1:1 basis with the same stratification as in the 1st randomization. The randomization schemes and identification for each subject will be included in the final clinical study report for this study.

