9.7.1.1.2 SECONDARY ENDPOINTS

The key secondary endpoints will be:

- Mean change from Study Baseline in sSE at Month 6
- Mean change from Study Baseline of sWASO at Month 6

Additional secondary endpoints will be:

- Mean change from Study Baseline of sSOL, of sSE, of sWASO and of sTST, at the beginning of treatment (mean of the 7 nights after the 1st dose in Period 1), at Month 1 and at Month 3
- Mean change from Study Baseline of sTST at Month 6
- Proportion of responders at Month 6 and Month 12, where sleep onset responder is defined as follows: sSOL at Study Baseline is ≥ 30 minutes and mean sSOL at 6 months is ≤ 20 minutes, and sleep maintenance responder is defined as follows: sWASO at Study Baseline is ≥ 60 minutes and mean sWASO at 6 months is ≤ 60 minutes and shows a reduction of > 10 minutes compared to Study Baseline.
- Change from Study Baseline in daytime functioning, assessed as the total score from the 4 items on daytime functioning, on the ISI, at Months 1, 3, and 6
- Change from Study Baseline on the FSS at Months 1, 3, and 6
- Ratings on the morning sleepiness item of the Sleep Diary, for:
 - The mean change from Study Baseline of the 1st 7 mornings after the 1st dose in Period 1 and Period 2

- The mean change from Study Baseline at: Month 1, Month 3, and Month 6
- The mean change from Study Baseline and from Period 2 Baseline (as appropriate) for subjects with 1, 3, 6, 9 and 12 months exposure (revised per Amendment 06)
- The mean change from Screening for the 1st 7 mornings and 2nd 7 mornings of the Follow-up Period
- Rebound insomnia endpoints as assessed from the Sleep Diary during the Follow-up Period (revised per Amendment 02)
 - Change from Screening of sSOL on each of the 1st 3 nights, mean sSOL of the 1st 7 nights, and mean sSOL of the 2nd 7 nights of the Follow-up Period
 - Change from Screening of sWASO on each of the 1st 3 nights, mean sWASO of the 1st 7 nights and mean sWASO of the 2nd 7 nights of the Follow-up Period
 - Proportion of subjects whose sSOL is longer than at Screening for each of the 1st 3 nights, or whose mean sSOL is longer than at Screening for 1st 7 nights or 2nd 7 nights of the Follow-up Period
 - Proportion of subjects whose sWASO is higher than at Screening for each of the 1st 3 nights, or whose mean sWASO is higher than at Study Baseline for the 1st 7 nights or 2nd 7 nights of the Follow-up Period
- Persistence of Effect

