9.7.1.6.2 SECONDARY EFFICACY AND PHARMACODYNAMIC ANALYSES

Key Secondary Efficacy Analyses (revised per Amendment 03)

The change from Study Baseline of key secondary endpoints sSE and sWASO at Month 6 comparing LEM5 and LEM10 to PBO will be analyzed using the same analysis method as the primary endpoint. The missing values will be imputed using a pattern mixture model utilizing MI assuming MNAR. The treatment comparison will be performed using contrasts. The p-value, LS means and the 95% confidence interval (CI) of the treatment differences will also be provided. (revised per Amendment 03)

Other Secondary Efficacy Analyses (revised per Amendment 03)

The other secondary efficacy endpoints (change from Study Baseline of the following for LEM5 and LEM10 compared to PBO; mean sSOL, mean sSE, mean sWASO and mean sTST at 1st 7 nights, Months 1 and 3; and mean sTST at Month 6; ISI total of 4 items of daytime functioning at Months 1, 3, and 6, and FSS score at Months 1, 3, and 6) will be analyzed using MMRM, assuming MAR. The FSS will also be analyzed for responders, including only those subjects who endorsed clinically significant fatigue at Study Baseline. (revised per Amendments 03 and 06)

The proportion of responders, separately for sSOL and sWASO, will be analyzed using the Cochran-Mantel-Haenszel test, adjusted for country and age group, after the 1st 7 nights and for the last 7 nights of treatment at the end of Months 1, 3, 6 and 12, for LEM5 and LEM10 compared to PBO.

Rebound insomnia is defined as worsened sleep relative to Screening after study drug treatment is completed. Sleep Diary data from the Follow-up Period will be compared to Sleep Diary data from the Screening Period to assess whether subjects experience rebound

insomnia. Specifically, a higher value for sSOL or sWASO during the Follow-up Period compared to the mean sSOL or sWASO value during the Screening Period will be considered worsened sleep.

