1.1.2 Secondary Objectives

Key Secondary Objectives

- Determine the efficacy of LEM5 and LEM10 compared to PBO on subjective sleep efficiency (sSE) after 6 months of treatment in subjects with insomnia disorder
- Determine the efficacy of LEM5 and LEM10 compared to PBO on subjective wake after sleep onset (sWASO) after 6 months of treatment in subjects with insomnia disorder

Additional Secondary Objectives

- Determine the efficacy of LEM5 and LEM10 compared to PBO on sSOL, sSE, sWASO, and subjective total sleep time (sTST):
 - over the 1st 7 nights of treatment
 - after 1 month of treatment
 - after 3 months of treatment
- Determine the efficacy of LEM5 and LEM10 compared to PBO on sTST at 6 months

- Evaluate the proportions of sleep onset and sleep maintenance responders to LEM5 and LEM10 compared to PBO as defined by response on sSOL or sWASO at 6 months and 12 months
- Evaluate the safety and tolerability of LEM5 and LEM10
- Evaluate the efficacy of LEM5 and LEM10 compared to PBO as measured by responses on the Insomnia Severity Index (ISI) and the Fatigue Severity Scale (FSS) after 6 months
- Evaluate rebound insomnia following discontinuation of treatment
- Evaluate morning sleepiness during and following completion of treatment
- Evaluate persistence of efficacy of LEM5 and LEM10 over 12 months

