3 STATISTICAL METHODS

All statistical analyses will be performed by the sponsor or designee. When all subjects have completed Treatment Period 1 (Period 1), all data will be unblinded to the sponsor. There will be 3 database locks. The first will be of Period 1 data only, where data up to and including the visit at Month 6 will be analyzed. The second will include all data (Period 1 and ongoing Period 2 data) after all continuing subjects have completed the Month 9 (Period 2) visit, all available data will be analyzed to support regulatory submissions. The third will include all data where the study has continued to completion.

For the Period 1 analysis, sponsor staff and certain designees (detailed in the Study Integrity Charter) will be unblinded to the treatment allocation; however, subjects, investigators, and site personnel will remain blinded. These are not considered formal interim analyses since the primary and key secondary efficacy endpoints are all at Month 6 (Period 1), and there is no placebo control group in Period 2. Therefore, no Type I error adjustment is needed for efficacy analysis.

All descriptive statistics for continuous variables will be reported using number of observations (n), mean (arithmetic unless otherwise specified), standard deviation (SD), median, minimum and maximum. Categorical variables will be summarized as number and percentage of subjects. In summaries for safety the denominator for all percentages will be the number of subjects in a given treatment group. sSOL will be log transformed in analyses unless otherwise stated.

All statistical tests will be based on the 5% level of significance (two-sided).

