3.4 Efficacy Analyses

Efficacy analyses for Treatment Period 1 will be performed on the FAS unless otherwise specified. Different baseline values will be used for endpoints defined during Treatment Period 1 (ie, Day 1 to Month 6) and during Treatment Period 2 (ie Month 7 to Month 12). Baseline values for each efficacy parameter are specified in [Section 6.1.1](#). The On-Treatment FAS will be used for the on treatment summaries produced by time on treatment.

Unless specified otherwise, all efficacy endpoints will be derived by calculating the average of weekly (7 days) diary parameter values ([Section 6.1](#)).

12-month LEM exposure data will be summarized by treatment (LEM5, LEM10) and duration of exposure (1 month [30 days], 3 months [90 days], 6 months [180 days], 9 months [270 days] and 12 months [365 days]). Treatment groups are LEM5 and LEM10, and include both (a) LEM Period 1 subjects on the On-Treatment Full Analysis Set using the change from Study Baseline and (b) LEM Period 2 subjects previously receiving PBO on the On-Treatment Full Analysis Set using the change from Period 2 Baseline. No hypothesis test will be performed for efficacy endpoints beyond the Month 6 visit.

The primary and key secondary endpoints comparisons are tested following the gate-keeping testing procedure described in [Section 3.3.3](#) to control for the overall type I error at the 0.05 significance level. The first primary efficacy endpoint comparison will be performed at the 0.05 significance level. The subsequent testings will only proceed if the previous test is statistically significant at the 0.05 level.

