 - The sleep onset responder is defined as: sSOL at Study Baseline (or Period 2 Baseline) is >30 minutes and mean sSOL at each month (Months 7, 8, 9, 10, 11 and 12) is ≤ 20 minutes,
 - The sleep maintenance responder is defined as: sWASO at Study Baseline (or Period 2 Baseline) is >60 minutes and mean sWASO at each month (Months 7, 8, 9, 10, 11

and 12) is ≤ 60 minutes and shows a reduction of >10 minutes compared to Study Baseline (or Period 2 Baseline).

The proportion of responders will be analyzed based on the subjects with sSOL > 30 minutes at the baseline for sSOL and separately the subjects with sWASO > 60 minutes at the baseline for sWASO.

- Morning sleepiness item of the Sleep Diary:
 - Change from Study Baseline of mean rating on morning sleepiness at the 1st 7 mornings after the 1st dose in Treatment Period 1, Month 1, Month 2, Month 3, Month 4, Month 5 and Month 6.
 - Change of mean rating on morning sleepiness from Study Baseline / Treatment Period 2 Baseline for 1st 7 mornings after the 1st LEM dose, 1, 3, 6, 9 and 12 months of exposure to LEM5 and LEM10. Data from subjects randomized to LEM5 or LEM10 at the start of the study will use Study Baseline, data from subjects who were re-randomized to LEM5 or LEM10 in Period 2 will use Treatment Period 2 Baseline. Change from Screening of mean rating on morning sleepiness of 1st 7 mornings and 2nd 7 mornings in Follow-Up Period.
- Rebound insomnia endpoints during the Follow-up Period as follows:
 - Change from Screening of sSOL on each of the 1st 3 nights, mean sSOL of the 1st 3 nights, mean sSOL of the 1st 7 nights, and mean sSOL of the 2nd 7 nights of the Follow-up Period
 - Change from Screening of sWASO on each of the 1st 3 nights, mean sWASO of the 1st 3 nights, mean sWASO of the 1st 7 nights and mean sWASO of the 2nd 7 nights of the Follow-up Period
 - Proportion of subjects whose sSOL is longer than at Screening by at least 5 minutes for each of the 1st 3 nights, mean sSOL of the 1st 3 nights, mean of the 1st 7 nights, and mean of the 2nd 7 nights of the Follow-up Period
 - Proportion of subjects whose sWASO is higher than at Screening by at least 5 minutes for each of the 1st 3 nights, mean sWASO of the 1st 3 nights, mean of the 1st 7 nights, and mean of the 2nd 7 nights of the Follow-up Period.

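### The Month 12 responder endpoint is decided on the Month 6 value in the endpoint lists and compared in the protocol with a placebo group that no longer exists; the SAP drops that test but leaves the conflicting text in place

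*Protocol*

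**What the plan says.** **Objective.** The protocol (synopsis and 8.2) and SAP 1.1.2 evaluate responder proportions "compared to PBO as defined by response on sSOL or sWASO at 6 months and 12 months".

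**Endpoint lists.** The protocol synopsis, protocol 9.7.1.1.2 and SAP 3.1.2 list "Proportion of responders at Month 6 and Month 12, where sleep onset responder is defined as follows". The rule that follows rests on one post-baseline value, "mean sSOL at 6 months is" at most 20 minutes, with a matching 6-month rule for sWASO. Baseline must be at least 30 minutes (sSOL) or at least 60 minutes (sWASO). No rule uses a Month 12 value.

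**Protocol analysis.** The synopsis and 9.7.1.6.2 specify a Cochran-Mantel-Haenszel test for the "last 7 nights of treatment at the end of Months 1, 3, 6 and 12, for LEM5 and LEM10 compared to PBO".

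**Treatment in Period 2.** Under protocol 9.4.3, "those previously randomized to PBO will be randomized to either LEM5 or LEM10 on an approximately 1:1 basis". SAP Section 3 states that "there is no placebo control group in Period 2".

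**SAP analysis.** SAP 3.4 says "No hypothesis test will be performed for efficacy endpoints beyond the Month 6 visit". SAP 3.4.2.4 limits the placebo comparison to the first 7 nights through Month 6. After that it decides response on "mean sSOL at each month (Months 7, 8, 9, 10, 11 and 12", with a matching rule for sWASO. It summarizes those proportions against two baselines (Study Baseline and Period 2 Baseline), with cut-offs of more than 30 and more than 60 minutes.

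**Declared changes.** SAP Section 5 does not mention the dropped Month 12 test. It refers to Table 1 for the full list, where the relevant entry says only that responders were clarified.

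**The concern.** The Month 12 responder proportion is a named secondary endpoint, and persistence of efficacy over 12 months is a secondary objective. Three things go wrong as the texts stand.

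- Read literally, the endpoint lists make a Month 12 responder the same person as a Month 6 responder, so the endpoint carries no information about Period 2.
- The protocol test and the objective need a placebo group at Month 12, and the design provides none. SAP 3.2.1 bases Full Analysis Set summaries on the randomized group, so a Month 12 placebo column would hold subjects taking lemborexant. A difference or its absence there says nothing about efficacy against placebo.
- The SAP text that would settle the matter brings in a second baseline and a different cut-off, while SAP 1.1.2 and 3.1.2 keep the conflicting objective and endpoint. A programmer or report author could follow any of these and cite the plan for it.

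**Working it through.** **1. The texts side by side**

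| Place | Value deciding Month 12 response | Baseline cut (sSOL / sWASO) | Month 12 comparison |
|---|---|---|---|
| Endpoint lists (protocol synopsis, 9.7.1.1.2; SAP 3.1.2) | 6-month mean | ≥30 / ≥60 min | not stated in the rule |
| Objectives (protocol synopsis, 8.2; SAP 1.1.2) | not stated | not stated | against placebo |
| Protocol synopsis and 9.7.1.6.2 | last 7 nights of Month 12 | no rule of its own | CMH test against placebo |
| SAP 3.4 and 3.4.2.4 | Month 12 mean | >30 / >60 min, two baselines | summary only, no test |

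That makes two response rules (the 6-month value and the visit's own value), one comparator that does not exist, and two unsettled details (cut-off and baseline).

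**2. Reproducing the stated responder power**

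Inputs from protocol 9.7.2 and SAP Section 2: 300 per arm, two-sided 0.05, differences of 16 points (onset) and 24.4 points (maintenance). The placebo rate is not given, so it is varied as an assumption.

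Power = Φ[(d − 1.96·se0)/se1], where se0 = √(2p̄(1−p̄)/n) and se1 = √([p1(1−p1)+p2(1−p2)]/n).

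For 15% against 31%: p̄ = 0.23, se0 = √(2×0.23×0.77/300) = 0.0344, se1 = √((0.1275+0.2139)/300) = 0.0337. Power = Φ[(0.16 − 0.0673)/0.0337] = Φ(2.75) = 99.7%.

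| Assumed placebo rate | Power, 16 points |
|---|---|
| 10% | 99.9% |
| 15% | 99.7% |
| 20% | 99.3% |
| 25% | 98.8% |
| 42% (worst) | 97.6% |

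For 24.4 points, power exceeds 99.99% at every rate. The plan's figure of more than 99% is therefore reproduced, for onset at placebo rates up to about 22.6%. It belongs to the 6-month definition that accompanies it in the text.

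**3. The same test at Month 12**

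Subjects taking placebo in Period 2: 0. If the arm randomized to placebo is used anyway, its continuing members have had about 6 months of lemborexant, against about 12 in the other arms. Assume a 31% rate in the arms on lemborexant from Day 1 and let the switched arm lag by an assumed amount. The rejection probability is the same normal approximation with both tails added. For a 4-point lag at 300 per arm: p̄ = 0.29, se0 = 0.0371, se1 = 0.0370, so Φ[(0.04 − 0.0726)/0.0370] + Φ[(−0.04 − 0.0726)/0.0370] = 0.189 + 0.001 = 19.0%.

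| Assumed lag | n = 300 | n = 150 | n = 120 |
|---|---|---|---|
| 0 points | 5.0% | 5.0% | 5.0% |
| 2 points | 8.3% | 6.6% | 6.3% |
| 4 points | 19.0% | 11.9% | 10.5% |
| 8 points | 59.8% | 34.4% | 28.6% |

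The 150 and 120 are the worst-case numbers remaining per group at Months 6 and 12 in protocol 9.7.2. SAP 3.4.2.4 also restricts the denominator to subjects above the baseline cut, so 300 is an upper limit. None of these probabilities is power against placebo.

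**The case against.** The strongest reply is that the SAP has already dealt with this. It confines the placebo comparison to Month 6 and earlier, bars later tests, states that Period 2 has no placebo control, and spells out that response is judged on each month's own mean. The protocol leaves further analytical detail to the SAP. On that reading the 6-month phrase in the endpoint lists is loose drafting carried over from the sample-size text, since the protocol applies the responder analysis at several visits and one fixed 6-month value would make them all identical. This largely stands: the invalid test should not be run if the SAP analysis text is followed.

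It is not a full answer. The SAP repeats the 6-month rule in 3.1.2 and the 12-month placebo objective in 1.1.2, and neither Section 5 nor Table 1 names the dropped test. Amendment 06 recast neighbouring Period 2 endpoints by duration of exposure, but the responder bullet and the test sentence carry no such mark.

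A reader might go further and infer any of the following, which the documents do not support:

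- *Three competing definitions of response, two giving a wrong 12-month result.* The protocol test sentence defines no responder rule and points to the Month 12 nights. Its proportion in the lemborexant arms can be right; its comparator is what fails.
- *Loss of response after Month 6 would go unseen.* SAP 3.4.2.4 gives responder proportions for every month from 7 to 12, and its persistence analyses compare the continuous measures through Month 12 with Month 1.
- *The trial would report no benefit over placebo at one year.* That needs the Month 12 test to be run and misread, and the SAP omits it.

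**Conclusion.** The concern holds as a conflict in the text that includes one invalid comparison. As written, the endpoint lists judge Month 12 response on the wrong visit, and the protocol and objectives promise a placebo comparison that the design cannot deliver. The SAP corrects both in its analysis text, without saying so plainly and while adding its own differences in cut-off and baseline.

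The absence of a placebo group at Month 12 follows from the design and needs no assumption. The rejection rates depend on an assumed 31% response rate and assumed lags, and serve only to show that such a test would not behave like a comparison with placebo. The power figure above 99% should be cited for Month 6 only.

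The consequence is contained. Responders lie outside the gate-keeping sequence and carry no multiplicity adjustment, so the primary and key secondary conclusions and the sample size do not change. The correction is worth making because the Month 12 responder rate is a listed secondary endpoint and currently has no single definition.

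**What to change.** - In the endpoint lists (protocol synopsis and 9.7.1.1.2; SAP 3.1.2), define response on the mean at the visit analysed: Month 6 for Month 6, Month 12 for Month 12.
- Remove Month 12 from the Cochran-Mantel-Haenszel comparison with placebo in the protocol synopsis and 9.7.1.6.2.
- In the objectives (protocol synopsis and 8.2; SAP 1.1.2), limit the placebo comparison to 6 months.
- Report the Month 12 proportion descriptively with a 95% CI. Make Study Baseline the main baseline for subjects randomized to lemborexant on Day 1.
- Use one baseline cut-off throughout, either inclusive or strict. The sample-size text in both documents uses the inclusive form.
- Name the dropped Month 12 test and any change of cut-off in SAP Section 5.

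The cost is wording, made through a protocol amendment and a SAP revision. No sample size or power figure changes. The claim of a 12-month placebo comparison is given up, but the design could not have supported it.

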9.7.1.6.3 EXPLORATORY EFFICACY AND PHARMACODYNAMIC ANALYSES

The change from Study Baseline for the mean score of the quality of sleep item on the Sleep Diary will be analyzed using MMRM, assuming MAR for the mean of the 1st 7 days of Period 1 and at Months 1, 3, and 6. (revised per Amendment 03)

Health-related quality of life: the change from Study Baseline for the EQ-5D-3L scores (both total score and Visual Analog Scale score), and the four scores from WPAI-GH will be using MMRM, assuming MAR for Month 1 (EQ-5D-3L only) and Months 3 and 6 (both EQ-5D-3L and WPAI-GH). (revised per Amendment 03)

Each item on the PGI-Insomnia at Months 1, 3, and 6 will be analyzed separately by calculating the number and percentages of subjects for each response category (eg, negative [3], neutral [2], positive [1] medication effect). The percentage of positive responses will be compared between treatment groups using the chi-square test, and repeated for age subgroups.

Summaries of all efficacy endpoints will be performed for 12 months exposure. Where appropriate, 95% CIs around the mean change from Study Baseline or Period 2 Baseline (for Period 1 and Period 2 data, respectively) will be presented. (revised per Amendment 06)

No multiplicity adjustment is planned for the exploratory and pharmacodynamic endpoints. (revised per Amendment 03)

9.7.1.7 Pharmacokinetic, Pharmacodynamic, and Other Biomarker Analyses

9.7.1.7.1 PHARMACOKINETIC ANALYSES

The Safety Analysis Set will be used for individual lemborexant and its metabolites M4, M9, and M10 plasma concentration listings. The PK Analysis Set will be used for summaries of lemborexant M4, M9, and M10, by dose, time, and day.

A population PK approach will be used to characterize the PK of lemborexant. For this approach, PK analysis data from this study will be pooled with relevant data from Phase 1 and 2 studies, and other Phase 3 studies if available. The effect of covariates (eg, demographics, concomitant medications) on the PK of lemborexant will be evaluated. The PK model will be parameterized for oral clearance (CL/F) and volumes of distribution. Derived exposure parameters such as AUC and C_{\max} of lemborexant and any other relevant parameters will be calculated from the model using the individual estimates parameterized for oral clearance and dosing history.

9.7.1.7.2 PHARMACODYNAMIC ANALYSES

There are no variables in this study that are primarily designated as PD variables. These analyses are described in the Secondary Efficacy and Pharmacodynamic Analysis [Section 9.7.1.6.2](#) and Exploratory and Pharmacodynamic Analyses [Section 9.7.1.6.3](#).

